## 10. Statistical considerations

### 10.1 Sample size

This is a single group study. No power calculation has been undertaken. The estimated sample six patients in whom cannulation is attempted following the twenty minute time out (see Section 8.5) was selected to allow robust data to support a future efficacy study.

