**Principal Investigator Name:** **[name]**

**Signature:** 

**Date:** **02 March 2022**

### 3. Summary and synopsis

Short Title	Sub30
Methodology	Feasibility study of a complex intervention
Research Sites	Barts Health NHS Trust London Ambulance Service NHS Trust
Objective/Aims	To establish whether a pre-hospital advanced physician/ paramedic cardiac arrest team that is ECMO capable can establish ECMO flow within 30 minutes of collapse
Number of participants	6 patients who are cannulated for ECMO
Inclusion and exclusion criteria	
Male and female patients with a known or visible age of 18 to 65 years who:
 
 
have a witnessed out-of-hospital cardiac arrest
 
a presumed cardiac aetiology to their cardiac arrest
 
receive bystander chest compressions within 3 minutes
 
remain in cardiac arrest at 20 minutes following collapse or fail to sustain ROSC in the pre-hospital setting
 
 
The following patients will not be suitable for ECMO:
 
 
Identified as or visibly less than 18 years or greater than 65 years
 
Known or visible advanced pregnancy (when resuscitative hysterotomy should be performed)
 
Evidence from others present at the scene or patient examination that ECMO unlikely to benefit patient (e.g. advanced frailty, advanced malignancy, ...).
 
No signs of life (physical movement or breathing) AND evidence of ineffective chest compressions suggested by: 
 
Absence of electrical activity OR
 
End tidal carbon dioxide level of less than 1.3 kPa (10 mmHg)
 
 
 
 
Out-of-hospital cardiac arrest encompasses both those who arrest prior to the emergency services being called and those who are witnessed to arrest by the emergency services. For the purpose of this study patients who suffer their first cardiac arrest whilst in transit to hospital will not be included.

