### 5. Study objectives

The study aims to test the hypothesis that a system that overcomes the logistical and technical barriers to minimise the collapse-to-ECPR interval and combines an ECMO team with advanced pre-hospital practitioners can establish patients in refractory cardiac arrest with ECMO flow (>50% target) within 30 minutes of collapse.

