3.7 Level of significance

The study is descriptive and no hypothesis tests will be conducted.

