3.8 Sample size

No power calculation has been undertaken. The study aims to recruit six patients. The sample size has been selected to allow robust data to support a future efficacy study.

4 General Analysis Definitions

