8.1 Method for analysis of endpoints

8.1.1 Analysis of primary endpoint

Analysis will be descriptive. Results will be presented as the total number, and the number and proportion of patients with ROSC or ECMO flow (>50% target) in the treated population.

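### The primary proportion from six patients should carry an exact 95% interval, on a denominator that keeps failed cannulations

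*Protocol*

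**What the plan says.** On sample size, Protocol 10.1 states: "This is a single group study. No power calculation has been undertaken". It then describes "The estimated sample six patients in whom cannulation is attempted following the twenty minute time out" and says that this number "was selected to allow robust data to support a future efficacy study". SAP 3.8 repeats the claim: "The sample size has been selected to allow robust data to support a future efficacy study". The protocol synopsis defines the six differently, as "6 patients who are cannulated for ECMO".

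On aim and inference, Protocol section 5 opens: "The study aims to test the hypothesis that a system that overcomes the logistical and technical barriers", and goes on to ECMO flow within 30 minutes of collapse. SAP 3.7 says: "The study is descriptive and no hypothesis tests will be conducted".

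On the primary analysis, SAP 8.1.1 says: "Results will be presented as the total number, and the number and proportion of patients" who reach the endpoint, taken in the treated population. SAP 4.1.3 defines that population as cannulated patients. Protocol 10.2 and SAP 8.1.2 plan medians, ranges, counts, proportions and raw categorical data. No interval is planned anywhere.

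On use of the result, Protocol 4.5 and SAP 2.2 say that a larger randomised trial is merited if the 30-minute target proves feasible, and that the data will help to estimate the size of any outcome benefit. Neither gives a proportion that would count as feasible.

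**The concern.** The sample size is justified by a property of the data, robustness, that no calculation supports. The primary result is then planned without any statement of precision. With six patients the observed proportion can take only seven values, and each is compatible with a wide range of true success rates. A reader designing the next trial needs that range as well as the count.

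The denominator makes this more pressing. If the proportion is taken only in cannulated patients, failed attempts drop out and the figure moves towards success. An interval placed on that figure would look exact but would describe a selected group.

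**Working it through.** **Is there a figure to reproduce?** No. The documents give no alpha, target rate, null rate or precision target, so no formula returns six. What can be computed is the precision that six patients give.

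**Inputs.** n = 6 (Protocol 10.1, SAP 3.8); x = number reaching the endpoint, 0 to 6; two-sided 95% level (my choice, since the documents set none).

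**Formula (Clopper-Pearson).** Lower limit = 2.5% quantile of Beta(x, n − x + 1). Upper limit = 97.5% quantile of Beta(x + 1, n − x). At the ends these simplify: for 6/6 the lower limit is 0.025^(1/6) = 0.541; for 0/6 the upper limit is 1 − 0.541 = 0.459.

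| Result | Proportion | Exact 95% interval | Width (points) |
|---|---|---|---|
| 0/6 | 0% | 0 to 45.9% | 46 |
| 1/6 | 16.7% | 0.4 to 64.1% | 64 |
| 2/6 | 33.3% | 4.3 to 77.7% | 73 |
| 3/6 | 50.0% | 11.8 to 88.2% | 76 |
| 4/6 | 66.7% | 22.3 to 95.7% | 73 |
| 5/6 | 83.3% | 35.9 to 99.6% | 64 |
| 6/6 | 100% | 54.1 to 100% | 46 |

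**Does the choice of interval matter?** Wilson intervals are narrower but lead to the same reading: 3/6 gives 18.8 to 81.2%, 5/6 gives 43.7 to 97.0%, 6/6 gives 61.0 to 100%.

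**The same point as chances (binomial, n = 6; assumed true rates).**
- True rate 50%: P(at least 4/6) = (15 + 6 + 1)/64 = 34%; P(at least 5/6) = (6 + 1)/64 = 11%.
- True rate 80%: P(fewer than 5/6) = 1 − (6 × 0.8^5 × 0.2 + 0.8^6) = 1 − (0.393 + 0.262) = 34%.

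A mediocre system can therefore look good, and a good one can look mediocre, each about one time in three.

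**Denominator.** Three places differ:
- Protocol 10.1 counts patients in whom cannulation is attempted.
- The synopsis counts patients cannulated. SAP 8.1.1, through SAP 4.1.3, does the same.
- SAP Table 3 lists the number cannulated within 30, 45 and 60 minutes under candidates at the 20-minute time-out.

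Suppose six attempts, one failed cannulation and four successes in time. On attempts the result is 4/6 = 66.7%; on cannulated patients it is 4/5 = 80.0%. Such a case is not remote. The risk table in Protocol section 9 expects 5 to 10% failure before mitigation. If attempts are independent, the chance of at least one failure in six is 1 − 0.95^6 = 26% at 5%, and 1 − 0.90^6 = 47% at 10%.

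**The case against.** The best reply is that this is a declared descriptive feasibility study and is consistent about it. It needs no power calculation, and its lack of one is stated openly. SAP 8.1.1 gives the total and the count as well as the proportion, and Protocol 10.2 presents categorical data raw, so every reader will see that the denominator is six and can compute an interval. Robust data may also refer to process data on dispatch, arrival times and guidewire attempts, some of which come from more than six people. The hypothesis in Protocol section 5 is a loose statement of capability with no null value, and no analysis depends on it.

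Much of this stands. A reader might infer that the result will be taken as more certain than it is, but with count and total shown the documents do not support that. A reader might also infer that this proportion alone decides whether a larger trial follows. Protocol 4.5 and SAP 2.2 tie that step to feasibility in general, attach no threshold, and sit beside secondary objectives on recruitment, safety, outcome and resources. Nor does the hypothesis wording show that a test is missing.

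What does not stand is that the interval is superfluous. Seeing 5/6 does not tell most readers that a true rate of 36% remains possible. An interval is estimation, so the rule against tests in SAP 3.7 does not exclude it.

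One objection limits the remedy. A binomial interval assumes a constant success probability, which is doubtful for a new team's first cases, and SAP 8.2 says that the analysis makes no assumptions. That calls for a stated caveat, not for omitting the interval.

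**Conclusion.** The point holds as a modest reporting improvement. The primary proportion is planned without a measure of uncertainty, and at n = 6 that uncertainty is 46 to 76 percentage points on the exact 95% scale. The claim of robustness has no stated basis, although the documents do not show it to be false for process data. The size and design of the study are not in question.

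The widths assume six patients in the denominator, independent patients and a constant success probability. If the synopsis definition governs recruitment and attempts exceed six, the widest possible interval would be slightly narrower, and the conclusion would be the same. The interval describes sampling uncertainty only. It does not supply the missing feasibility threshold, and it does not reconcile the differing endpoint definitions (ECPR from collapse in Protocol 5.3; ROSC or flow from the start of chest compressions in SAP 3.4).

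**What to change.** 1. **SAP 8.1.1:** report x/n with an exact (Clopper-Pearson) 95% confidence interval. Take n as all patients in whom cannulation is attempted after the 20-minute time-out, as in Protocol 10.1, so that a failed cannulation counts as not reaching the endpoint. Align the synopsis and SAP 4.1.3 with this.
2. **SAP 8.2:** state that the interval assumes independent patients with a common success probability, and that this is uncertain while a new team gains experience.
3. **Protocol 10.1 and SAP 3.8:** replace the robustness claim with the precision, for example: with six patients the exact 95% interval for the primary proportion will be between 46 and 76 percentage points wide.
4. **Protocol section 5:** reword the aim as estimating the proportion, to agree with SAP 3.7.

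Items 3 and 4 are accompanying edits; item 1 carries the benefit. The cost is a few lines in each document, with no extra patients, data or test. The downside is that the stated claim becomes less favourable: the sample size is openly described as imprecise, and failed attempts can lower the reported proportion.

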### 10.2 Methods of Analysis

Data will be analysed using a combination of Excel for Mac 2016 (Microsoft Corporation), Prism 5 (GraphPad software) and R. Summary data will be presented as a median and range for all six patients. Categorical data will be presented as raw data.

Patient mortality will be compared to other patients who were managed by LAS on non-study days. These data are stored in a bespoke Cardiac Arrest database, for which London Ambulance Service NHS Trust is the Data Controller. Only patients cared for concurrently with this study will be used for matching. London Ambulance Service NHS Trust will provide these data to the Chief Investigator after the last patient has been enrolled.

Patients will be matched based on their likelihood of receiving ECMO on a one to many basis. Potential matches will be first screened for the study inclusion and exclusion criteria. A priori defined factors that may be used to estimate this likelihood of receiving are:

- age (closest match to 5 years)
- time of first LAS resource attendance on scene (closest match to 5 minutes)
- presumption of a cardiac aetiology to the arrest

Three techniques will be used in matching – individual matching, propensity score matching and GenMatch matching. Matching will be undertaken with replacement. Missing data will not be imputed.

## 11. Ethical and regulatory considerations

### 11.1 Protocol

This protocol was constructed in line with the SPIRIT 2013 recommendations [22]. Approval of the protocol was granted by the Trial Steering Committee.

### 11.2 Peer review

Independent expert peer reviews of this protocol were sought from:

- The Barts Heart Centre Peer Review Committee
- The international ECMO Network (ECMONet)

### 11.3 Management of actual and potential conflicts of interest

The guidelines of the International Committee of Medical Journal Editors will be used for disclosures of any conflicts of interest (financial and non-financial). Each investigator and member of TSC or DSMC must disclose any conflicts of interest prior to commencing the study. These data will be included in the Trial Master File and be renewed every six months. Any reported conflict will be discussed with the Sponsor and Funders.

### 11.4 Summary of main ethical, legal and management issues

The main ethical considerations are:

- Emergency enrolment of patients who lack the capacity to provide consent

Patients are unable to provide consent to enter the study at the point of enrolment as they lack capacity since they are unconscious and in cardiac arrest. This situation is sudden and unexpected preventing prior consultation with the patient and prospective consent. Their capacity will not vary throughout the intervention period as they will remain in cardiac arrest

and unconscious. Since there are no alternative groups of patients in whom this study could be conducted it is necessary to recruit patients who lack capacity.

If it were possible to find a personal consultee for the patient, it is unlikely that the consultee could make an informed decision about the study in the limited time available and in the context of the distress of learning the patient is in cardiac arrest.

Since even short delays in resuscitation and emergency treatments are associated with worse patient outcomes, there is insufficient time to find and contact a professional consultee such as the patient's general practitioner.

Finally, it is considered that since the intervention is likely to benefit the patient directly and that this is proportional to the burden of taking part; particularly in the context that they are in cardiac arrest and have a rate of survival of less than 10% without any additional intervention.

If established, ECMO support will be life-sustaining. Therefore a personal consultee will not be asked if the participant should remain in the study. Nevertheless, they will be consulted about the patient's other medical conditions and likely wishes and these will be considered, according to standard clinical practice, by the attending physicians who will not be study investigators. Family and friends of study participants will be given information about the study as soon as is practicable in the form of face to face discussions and information leaflets.

Participants will be approached if they regain capacity to inform them of their participation in the study. This will be done prior to hospital discharge and usually be on the hospital ward when they are no longer critically unwell. Individual patients can ask to be withdrawn from the study if they request to do so. The patient will not be required to provide a reason for wanting to withdraw from the study. Withdrawal from the study will not influence the goals of on-going medical care for that patient.

If patients never regain capacity due to death or severe neurological injury then they will never be an opportunity to ask them about their inclusion in the study. We will retain and process any data collected about the patient within the constraints outlined the General Data Protection Regulation. We will retain some of the excess plasma and serum collected as part of routine clinical measurements during the clinical care of the patient.

- Are the results generalisable to other geographical areas?

This feasibility trial involves a collaboration between Barts Health, London Ambulance Service and London's Air Ambulance. These are three well-resourced institutions who have established the logistics to deliver very rapid emergency pre-hospital care in London. If the study demonstrates it is feasible to deliver ECPR within 30 minutes in London, is this generalisable to other urban and non-urban areas?

A key aspect of this study design is testing the training and simulation that has developed the new ECMO team and these will translate to other geographic areas. It is very likely that other urban centres will be able to replicate the service. We have been approached by other centres keen to participate in a multicentre outcome study if feasibility is demonstrated.

By contrast, it may take longer for an ECMO team to attend patients in non-urban settings due to the distances that need to be covered but in part mitigated by reduced traffic. Whilst a 30 minute threshold may not be possible in these settings although the processes and lessons learnt may enable accelerated ECPR in these settings too. This parallels the different provision in rural areas for other service such as major trauma centre access or emergency primary coronary intervention access.

- ECPR may increase survival but with neurological injury

If ECPR restores blood flow to the patients' vital organs such as the heart, liver, brain, kidneys and gut it is possible that this is sufficient to enable the patient to survive but insufficient to prevent brain injury. However, observational data from patients who receive

ECPR suggest that the proportion of surviving patients without severe neurological injury improves. Nevertheless this question will be a core question of any outcome study if the current study demonstrates the feasibility of the intervention.

- Maintenance of patient dignity and privacy in the pre-hospital setting

We specifically asked at a public engagement event about patient dignity and the impact of a procedure which required insertion of plastic tubes into the groin and exposure of the patient's lower abdomen, pelvis and upper thighs. The universal opinion was that this was unavoidable and outweighed by the potential benefits of the intervention. We will endeavour to maintain patient dignity by utilising windowed drapes that will cover a patient again apart from a small region in the upper thigh. Moreover, the paramedics and pre-hospital physicians in this study are well versed in scene control and will manage bystanders appropriately. They are often assisted in this by the simultaneous attendance of the police in public areas.

- ECPR may impede standard ALS algorithms

Institution of ECPR could impede standard ALS algorithms as pipes are inserted into the femoral vessels. Our protocol does not involve any interruption of conventional resuscitation which will continue for at least 20 minutes – the time period when a return of spontaneous circulation (ROSC) is most likely and a scenario that is best for the patient. Following 20 minutes the number of patients who go on to survive without disability are few and proportionally reducing rapidly. By contrast the number of patients who go on to die or who have severe disability are many and increasing rapidly. This justifies the addition of an alternative resuscitation strategy to augment the continued standard resuscitation algorithms. Most ambulance services in England follow the European Resuscitation Council guidelines for pre-hospital resuscitation, which advise at least 20 minutes of CPR for all attempted resuscitations. If there is failure to achieve ROSC and the cardiac rhythm is asystole, then the resuscitation is terminated typically. Resuscitation may also be stopped if the cardiac rhythm is pulseless electrical activity (PEA) after discussion with a clinical support desk. If the rhythm is refractory ventricular fibrillation/tachycardia, the patient will be transported with on-going CPR to the nearest emergency department or heart attack centre.

- Pre-hospital ECPR may be associated with a higher risk of procedural complications

Undertaking a complex in-hospital procedure in the pre-hospital environment could potentially increase the risk of complications from the procedure. We have completed a complex risk assessment matrix within our protocol and have introduced measures to reduce all risks. In published reports of pre-hospital ECPR, the complication rates are no more than that of in-hospital ECPR.

An alternative strategy to institute ECPR earlier is to start moving the patient the hospital to earlier (colloquially called to 'scoop and run'). Since it is not possible to prospectively identify patients who cannot be resuscitated within 20 minutes, this strategy will require all patients to be transported immediately to hospital with chest compression continuing en route. Evidence has demonstrated that CPR is inferior during transport and therefore such a strategy would risk potential early ROSC in patients by delivering sub-optimal resuscitation in a bid to shorten transfer times.

## 11.5 Research Ethics Committee (REC) review and reports

The Chief Investigator (CI) has obtained approval for this study from the London Harrow NHS Research Ethics Committee. The study will be submitted for Site Specific Assessment at St Bartholomew's Hospital. The Chief Investigator will require a copy of the Site Specific Assessment approval letter before the study can commence.

All substantial amendments that require review by the REC will not be implemented until the REC and Sponsor grant a favourable opinion regarding the amendment.

All correspondence with the REC will be retained in the Trial Master File. It is the Chief Investigator's responsibility to provide an annual progress report will be submitted to the REC within 30 days of the anniversary date on which the favourable will was given, and annually until

the trial is declared ended (Section 7.9) The CI will notify the REC when the trial ends, even if this is early. In the context of early discontinuation, the REC should be informed of the reasons for this. The CI will be responsible for submitting a final report within one year of the end of the study, indicating the results and any publications or abstracts to date.

## **11.6 Annual Safety Reporting**

The CI will send an Annual Progress Report to the REC and the sponsor using the Health Research Agency template on the anniversary of the REC “favourable opinion”.

## **12. Public Involvement**

Patients and publics were involved in the design of this study through a Patient and Public Engagement event held at 2 May 2017. Specific questions asked in addition to a general open session centred around:

- concerns about consent and permission to enter a study when patient lacks capacity since they are in cardiac arrest
- concerns about preserving patients' dignity, autonomy, and privacy in the context of resuscitation that is happening outside a healthcare setting
- appropriate outcome measures that may demonstrate benefit or harm
- communication of the study to a wider audience

A lay person will be asked to join the Trial Steering Committee and will contribute to the discussions on the study management and dissemination of findings.

The study will be registered with the INVOLVE open-access database which registers healthcare projects involving members of the public as partners in the research process (<http://www.invo.org.uk>).

